## 14.2 Benefits and Risks: Clinical

The ability of ataluren to enable readthrough of nonsense mutations has been clinically demonstrated in other indications of nonsense mutation-mediated disease (Kerem 2008, Sermet-Gaudelus 2010, Wilschanski 2011, Finkel 2013). Ataluren's effect in treatment of nmDMD has been demonstrated (Bushby 2014), and in July 2014 ataluren was approved by the EMA for treatment of nmDMD. In addition, in a Phase 3 study of nmCF subjects, ataluren-treated subjects had less lung function decline and fewer pulmonary exacerbations than placebo-dosed subjects (Kerem 2014).

Totaling all ataluren clinical studies, including healthy volunteers as well as subjects with several nonsense mutation genetic disorders, >750 subjects have been exposed to ataluren in Phase 1 (Hirawat 2007), Phase 2 (Kerem 2008, Sermet-Gaudelus 2010, Wilschanski 2011, Finkel 2013) and Phase 3 (Bushby 2014, Kerem 2014) clinical studies. Ataluren has shown a favorable safety profile in clinical studies.

Approximately 40% of patients with aniridia have a nonsense mutation in one allele of the PAX6 gene (Tzoulaki 2005). Because ataluren-induced readthrough of nonsense mutations has been demonstrated in Phase 2 and Phase 3 clinical studies of other nonsense mutation genetic diseases, while showing a favorable clinical safety profile, it can be expected that ataluren treatment of nonsense mutation aniridia will exhibit acceptable benefit vs risk.

### 14.2.1 Justification for Inclusion of Minors

In standard toxicology studies, dosing is initiated in young adult rats (6 to 8 weeks old) and in 4-to 6-month old dogs. However, the chronic toxicology studies conducted with ataluren initiated dosing in weanling animals (approximately 4- to 5-week-old rats, and dogs <3 months of age) to support dosing of pediatric subjects as young as two years of age. A detailed summary of methods and results of these chronic toxicity studies is provided in Section 7 of the ataluren investigator's brochure.

In the clinic, ataluren has already been administered to subjects as young as three years old. A Phase 2 study of ataluren in subjects with methylmalonic acidemia (MMA) enrolled 11 subjects, including two subjects who were three years old and one subject who was 4 years old. All three of these subjects completed the study as planned, receiving ataluren 5, 5, 10 mg/kg for 28 days in Cycle 1 and ataluren 10, 10, 20 mg/kg for 28 days in Cycle 2; there was a washout period of 21 days between the cycles.

Ataluren was well tolerated by the three subjects <6 years old in the MMA study. Treatment-emergent adverse events in these subjects were vomiting, pyrexia, nasopharyngitis, cough, flatulence, and rash. All treatment-emergent adverse events were mild or moderate in severity, and none were serious or led to discontinuation of treatment. Overall, the ataluren safety profile was similar in <6 years old and ≥6 years old.

Twenty-four-hour blood sampling for ataluren PK assessments was performed on Day 28 of each cycle; the data from Cycle 2, in which a dose of 10, 10, 20 mg/kg was administered, are of particular relevance to the proposed study in nonsense mutation aniridia. Ataluren plasma concentrations in the 3 subjects <6 years old were comparable to ataluren plasma concentrations in the 8 subjects ≥6 years old who participated in this study. Mean area under the curve (AUC)0-24h was 279.3 h•µg/mL and 358.4 h•µg/mL for subjects <6 and ≥6 years old, respectively, on Day 28 of Cycle 2. Mean maximum concentration (Cmax) was 28.2 µg/mL and 29.9 µg/mL for subjects <6 and ≥6 years old, respectively, on Day 28 of Cycle 2 (10, 10, 20 mg/kg). These data suggest similar ataluren PK profiles in subjects <6 and ≥6 years old.

Based on the above considerations, inclusion of young children in this protocol is appropriate. Furthermore, there has been careful consideration of the study design, wherein measures have been taken to minimize the number of subject visits and blood draws while maximizing the amount and quality of data required to effectively achieve the study objectives.

Study of young children is important given the onset of disease in early childhood, the importance of intervention when the disorder is still in its early phases, the limited treatment options that are currently available for this condition, and ataluren's favorable benefit/risk profile.

### 14.3 Benefit/Risk Conclusions

Aniridia is a devastating disease wherein patients have multiple ocular pathologies and become progressively visually handicapped. Current therapeutic approaches to treat aniridia are limited in efficacy, such as surgical management of cataracts and glaucoma treatments to relieve intraocular pressure. These treatments do not correct the anatomical defects associated with aniridia nor halt the progressive decline in visual acuity. There is a high unmet medical need for an effective treatment for aniridia.

Evaluation of ataluren as a treatment for nonsense mutation aniridia has sound scientific rationale founded on activity data from nonclinical disease models and clinical data from subjects with other genetic diseases, including efficacy and safety data from Phase 2b/3, placebo-controlled trials in nmDMD and nmCF. The safety profile of ataluren is supported by safety pharmacology and toxicology studies of appropriate type and duration, and by Phase 1, Phase 2, and Phase 3 safety data obtained in children and adults; the development program has identified potential clinical safety risks and appropriate monitoring strategies are included in the clinical studies.

Given the seriousness of aniridia and the limitations of available therapies, the aggregate potential benefits relative to the potential risks support further development of ataluren in this disease.

## 16 APPENDICES

### 16.1 Protocol Amendment History

Changes in Version 6.0 (08 Nov 2018) to Version 7.0 (17 DEC 2019)

**Justification for the amendment:** Due to the continuing unavailability of any treatment options targeting the underlying cause of nonsense mutation aniridia, a very small disease population, and the enrollment challenges that were encountered during the study, PTC Therapeutics amended the protocol, changing the primary endpoint from safety to efficacy in order to investigate the clinical utility of intervention with ataluren in the current study. The revised primary endpoint is the change from baseline (Visit 2/Day 1) to Week 48 in Maximum Reading Speed of OU as measured using the MNREAD Acuity Charts, [REDACTED] Maximum Reading Speed is a person's reading speed when reading is not limited by print size and is a measure that reflects the dynamic nature of reading. Maximum Reading Speed is known to be reduced when foveal vision is degraded, such as is seen in patients with aniridia. The primary objective was amended accordingly to reflect this change in primary endpoint. Additionally, the characterization of the systemic and ocular safety profile of ataluren in subjects with nonsense mutation aniridia was moved from being the primary objective to one of the secondary objectives. A corresponding secondary safety endpoint was added to reflect this change.

Summary of Protocol Changes			
Item No.	Protocol Section(s)	Update	Rationale
1	Protocol	Text modified	Document date and protocol version number were updated where they occurred; visual acuity was specified to be best corrected visual acuity (BCVA) where applicable; abbreviations and references were updated as needed; minor editorial revisions were incorporated throughout to provide clarity.
2	Synopsis	Text added	A protocol synopsis was included in this version (7.0) of the protocol.
3	Section 1.1 Introduction and Section 2.2.1 Therapeutic Rationale	Text modified	The number of times ataluren was renewed by the EMA was updated.
4	Section 3.1.1 Primary Objective	Text modified	Text was modified to reflect the change in primary objective from "to characterize the systemic and ocular safety profile of ataluren when administered chronically in subjects with nonsense mutation aniridia" to "to evaluate the effect of ataluren on Maximum Reading Speed as measured using the Minnesota Low Vision Reading Test (MNREAD) Acuity Charts in subjects with nonsense mutation aniridia".
5	Section 3.1.2 Secondary Objectives	Text added	Text added to reflect the modification of the secondary objectives to include the effect of ataluren on the Reading Accessibility Index, Critical Print Size and Reading Acuity and the systemic and ocular safety profile of ataluren in subjects with nonsense mutation aniridia.

Summary of Protocol Changes			
Item No.	Protocol Section(s)	Update	Rationale
6	Section 3.1.3 [REDACTED]	Text deleted	Text deleted to reflect the removal of MNREAD as one of the [REDACTED].
7	Section 3.2.1 Primary Endpoint	Text modified	Text modified to reflect the change in primary endpoint to “change from baseline (Visit 2/Day 1) to Week 48 in Maximum Reading Speed of OU as measured using the MNREAD Acuity Charts”.
8	Section 3.2.2 Secondary Endpoints	Text added/moved	Text added/moved to reflect the addition of key secondary endpoints: “change from baseline (Visit 2/Day 1) to Week 48 in Reading Accessibility Index of OU” and “change from baseline (Visit 2/Day 1) to Week 48 in BCVA”. Text added to reflect the addition of secondary efficacy endpoints related to Reading Accessibility Index, Maximum Reading Speed, Critical Print Size and Reading Acuity associated with the change in primary endpoint. Text added to reflect the addition of a secondary safety endpoint of assessments related to the systemic and ocular safety profile of ataluren in subjects with nonsense mutation aniridia.
9	Section 3.2.3 [REDACTED]	Text added/deleted	[REDACTED]
10	Section 8.3.15 MNREAD	Text added	Text added to further elaborate on the endpoints Maximum Reading Speed and Reading Accessibility Index.
11	Section 11.7 Efficacy	Text modified	Text modified to reflect change in primary endpoint and secondary efficacy endpoints and associated analysis shown in Sections 3.2.1 and 3.2.2.
12	Sections 11.7 Efficacy, 11.8 Safety and 11.9 [REDACTED]	Text moved	Sections were re-arranged to reflect changes to the primary endpoint from being a safety endpoint to an efficacy endpoint.
13	Section 11.13 Multiplicity	Text added	Text added describing multiplicity.
14	Section 13.2.2 Duration of Therapy	Text modified	Text modified to reflect changes to the primary and secondary objectives.
15	Section 13.2.3.3 MNREAD	Text modified	Text modified to include more detail about the new primary endpoint “change from baseline (Visit 2/Day 1) to Week 48 in Maximum Reading Speed of OU as measured using the MNREAD Acuity Charts”.

[REDACTED]

[REDACTED]

[REDACTED]

[REDACTED]

[REDACTED]

[REDACTED]

[REDACTED]

[REDACTED]

[REDACTED]

[REDACTED]

[REDACTED]

[REDACTED]

[REDACTED]

[REDACTED]

[REDACTED]

[REDACTED]

[REDACTED]

[REDACTED]

[REDACTED]

[REDACTED]

[REDACTED]

[REDACTED]

[REDACTED]

[REDACTED]

[REDACTED]

[REDACTED]

[REDACTED]

[REDACTED]

[REDACTED]

[REDACTED]

[REDACTED]

[REDACTED]

1 INTRODUCTION

This statistical analysis plan (SAP) outlines the proposed statistical methods to be implemented in the analysis of data collected within the scope of PTC Therapeutics, Inc. Protocol PTC124-GD-028-ANI, “STAR: A Phase 2, Multicenter, Randomized, Double-Masked, Placebo Controlled Study of the Safety and Efficacy of Ataluren (PTC124) for the Treatment of Nonsense Mutation Aniridia,” protocol, Version 7, dated 17 December, 2019.

It is not intended that each and every table, listing, or graph will be included in the clinical study report (CSR). It is also possible that additional analyses will be conducted after review of the data. Any analyses or summaries not specified in the SAP, but performed after review of the data, will be identified in the CSR as post hoc.

2 OBJECTIVES

2.1 Primary

The primary objective of this study is to evaluate the effect of ataluren on Maximum Reading Speed as measured using the Minnesota Low Vision Reading Test (MNREAD) Acuity Charts in subjects with nonsense mutation aniridia.

2.2 Secondary

The secondary objectives of this study are to:

- Evaluate the effect of ataluren on the following:
 - Reading Accessibility Index
 - Best-corrected visual acuity (BCVA)
 - Critical Print Size
 - Reading Acuity
 - Severity of corneal keratopathy
 - Iris area
- Characterize the systemic and ocular safety profile of ataluren in subjects with nonsense mutation aniridia.

2.3

[REDACTED]

[REDACTED]

- [REDACTED]
- [REDACTED]
- [REDACTED]
- [REDACTED]
- [REDACTED]

█	█
█	█
█	█
█	█
█	█

2.4 Study Design

This is a Phase 2, multicenter, stratified, randomized, double-masked, placebo-controlled study with a 4-week screening period, a 144-week treatment period, an optional 96-week open label sub-study, and a 4-week post-treatment follow-up period (either study completion or early termination). A minimum of 36 subjects with nonsense mutation aniridia who are ≥ 2 years of age are planned for enrollment into this study at investigator sites in US and Canada.

During the 4-week screening period, subjects will be assessed for eligibility.

Eligible subjects will enter the 144-week treatment period consisting of two stages:

- Stage 1 (Weeks 1 to 48) during which subjects will receive either ataluren or placebo in a masked fashion;
- Stage 2 (Weeks 49 to 144) during which subjects will receive open-label ataluren.

Eligible subjects will be randomized in a masked 2:1 fashion to either ataluren or placebo. Randomization will be stratified by age: ≤ 10 years versus > 10 years. Masked study drug will be dosed three times a day: 10 mg/kg in the morning, 10 mg/kg at midday, and 20 mg/kg in the evening for 48 weeks. Subjects (or parent/legal guardian) will record each dose on a diary card provided by PTC Therapeutics.

After completion of the Stage 1 (Week 48), subjects will be eligible for an additional 96 weeks of open-label ataluren treatment. Subjects who received ataluren during Stage 1 will continue to receive ataluren; subjects who had been randomized to placebo will receive ataluren during Stage 2

There will be an optional sub-study at the end of the Stage 2 Open-Label Extension. Subjects will be able to consent to receive an additional 96 weeks of ataluren treatment, returning to the clinic every 24 weeks. The assessments to be conducted are outlined in the schedule of events. Subjects who choose not to participate in the sub-study will be required to complete the Post-treatment follow-up visit at the end of the Stage 2 Open-Label Extension.

[figure not shown]
The start of the sub-study will require prior approval of a protocol amendment from applicable Institutional Review Boards and will continue for 96 week or until commercial availability of ataluren for this indication, whichever is first, or until a positive risk-benefit assessment in this indication is not demonstrated.

After the subject's last dose of ataluren, there will be a 4-week post-treatment follow-up period. A primary analyses of the double-masked phase will be conducted after the last subject has completed Week 96.

Subjects who complete the parent study will be eligible to participate in the sub-study. The principal investigator or sub-investigator will discuss the possibility of participation directly with study subjects and/or parent/legal guardian in the clinic.

A schematic of the study design is provided in [Figure 1](#).

Figure 1. STAR Aniridia Study Schematic

2.5 Sample Size

The study was planned to enroll a minimum of 36 subjects with nonsense mutation aniridia who are ≥ 2 years of age. This number of subjects has been reduced to 24 and should provide adequate information for an initial evaluation the efficacy safety of ataluren in this population.

3 STUDY ENDPOINTS

3.1 Primary Endpoint

The primary endpoint of this study is the percent change from baseline (Visit 2/Day 1) to Week 48 in Maximum Reading Speed of OU as measured using the MNREAD Acuity Charts.

3.2 Secondary Endpoints

The key secondary efficacy endpoints of this study are:

- Change from baseline (Visit 2/Day 1) to Week 48 in Reading Accessibility Index of OU
- Change from baseline (Visit 2/Day 1) to Week 48 in BCVA

Other secondary efficacy endpoints of this study are as follows:

- Percent change from baseline (Visit 2/Day 1) to Week 48 in Maximum Reading Speed of OD and OS
- Change from baseline (Visit 2/Day 1) to Week 48 in Reading Accessibility Index of OD and OS
- Change from baseline (Visit 2/Day 1) to Week 48 in Critical Print Size of OU, OD and OS
- Change from baseline (Visit 2/Day 1) to Week 48 in Reading Acuity of OU, OD and OS
- Change from baseline (Visit 2/Day 1) to Week 48 in severity of corneal keratopathy
- Change from baseline (Visit 2/Day 1) to Week 48 in iris area
- Change from baseline (Visit 2/Day 1, Stage 1) to Week 240 (Sub-study End of Treatment Visit) in BCVA. Note: This endpoint will be assessed only for the cohort of subjects who enroll into the sub-study.

The secondary safety endpoint of this study is the overall systemic and ocular safety profile of ataluren as determined by:

- Incidences of treatment-emergent adverse events (TEAEs)
- Abnormal findings on laboratory assessments
- Vital signs
- Physical examinations
- Ophthalmoscopy
- Slit-lamp examination
- Visual field testing

3.3

[REDACTED]

[REDACTED]

[REDACTED]

[REDACTED]

[REDACTED]

[REDACTED]

[REDACTED]

[REDACTED]

[REDACTED]

[REDACTED]

[REDACTED]

[REDACTED]

[REDACTED]

[REDACTED]

[REDACTED]

[REDACTED]

[REDACTED]

[REDACTED]

[REDACTED]

[REDACTED]

[REDACTED]

[REDACTED]

[REDACTED]

[REDACTED]

[REDACTED]

[REDACTED]

[REDACTED]

[REDACTED]

[REDACTED]

[REDACTED]

[REDACTED]

[REDACTED]

4 HYPOTHESES

1) Percent change from baseline (Visit 2/Day 1) to Week 48 in Maximum Reading Speed (MRS) of OU as measured using the MNREAD Acuity Charts:

Null Hypothesis: $\mu_A = \mu_P$
Alternate Hypothesis: $\mu_A \neq \mu_P$

Where μ_A = mean percent change in MRS in ataluren arm; μ_P = mean percent change in MRS in placebo arm.

5 DEFINITIONS

Adverse Event

An adverse event (AE) is any untoward medical occurrence associated with the use of a drug (investigational medicinal product) in humans, whether or not it is considered related to the drug. An adverse event can therefore be any unfavorable and unintended sign (including an abnormal laboratory finding), symptom, or disease in a study subject who is administered study drug in this study. A specific list of occurrences that should be reported as AEs is provided in section 9.1.1 of the study protocol. Subjects must be followed for adverse events for at least 28 days after the last dose of ataluren administration, or until any drug-related adverse events and/or ongoing serious adverse events (SAEs) have resolved or become stable, whichever is later. Any event that starts within 35 days (to account for visit window) after last dose of ataluren will be summarized.

Adverse events will be graded for severity using Common Terminology Criteria for Adverse Events (CTCAE) Version 4 grading, where 1=Mild, 2=Moderate, 3=Severe, 4=Life-threatening, and 5=Fatal.

Relationship to study treatment will be coded using the following categories: Unrelated, Unlikely related, Possibly related, and Probably related. In summaries where relatedness is dichotomized to related or not, Unrelated and Unlikely related will be classified as not related and Possibly related and Probably related will be classified as related.

Serious Adverse Event:

A serious adverse event is defined as an adverse event that

- Results in death
- Is life-threatening (patient is at immediate risk of death from the event as it occurred)
- Requires in-patient hospitalization (formal admission to a hospital for medical reasons) or prolongation of existing hospitalization
- Results in persistent or significant disability/incapacity
- Results in a congenital anomaly/birth defect

Treatment-Emergent AE:

A TEAE is any AE that begins or increases in severity after the initial dose of study drug and within 5 weeks of the last dose of study drug.

Age

Subject's age is defined as from date of birth to randomization date. The formula used is (randomization date – date of birth+1) / 365.25.

Ataluren Exposure

The duration of exposure to ataluren treatment is defined as the last dose date minus the first dose date + 1 day.

Baseline

For any variable, unless otherwise defined, baseline is the last assessment taken prior to the first study drug administration.

Change from Baseline

The arithmetic difference between a post-baseline value and the baseline value:

Change from Baseline = (Post-baseline Value – Baseline Value)

Percentage Change from Baseline = [(Post-baseline Value – Baseline Value) / Baseline Value] x 100

End of Double-masked study period

End of double-masked study period is at Week 48 (day 337 ± 28 days), unless terminated early.

End of Study

End of study is at Week 144 (day 1008 ± 7 days), unless terminated early.

Early termination from study

Early termination would be assigned to the visit whose visit window included the termination date. In the event that an early termination visit does not fall within a nominal visit window, then the termination visit will be assigned to the visit closest to that date. If duplicate data result from the assignment of a termination visit, then the values measured last will be selected for analysis.

Enrollment date

Enrollment date will be assigned after confirmation of eligibility has been received from PTC Therapeutics, but not after the first day of study drug administration.

Study drug

Study drug in this study is ataluren (PTC124) or placebo.

Randomization date

Randomization date is the day the subject is assigned a randomization number on study Day 1.

Study Day 1

Day 1 is defined as the first day that study drug is administered to the subject.

Study Day

Day on study = Starting from Day 1

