#### 8.1.1.2 Visit 2 (Baseline, Week 1 ±1 Day)

After the 4-week Screening period, subjects who continue to meet all eligibility criteria will complete the Baseline Visit (Visit 2/Week 1) as follows:

- Record any adverse events occurring since last visit and any that occur during this visit
- Record any changes in concomitant medications
- Physical examination
- Height and weight
- Vital signs (including systolic and diastolic blood pressure, radial pulse rate, and body temperature): performed after the subject has been in a sitting position for 3 - 5 minutes
- Complete the following ophthalmological assessments:
  - [REDACTED]
  - Ophthalmoscopy examination
  - BCVA and refraction
  - Slit-lamp examination - Slit-lamp examination should precede [REDACTED] measurement
  - Slit-lamp photography. The Reading Center manual should be referenced for detailed instructions regarding macro photography
  - OCT/Fundus photography - Anterior and posterior segment OCT and fundus photography will be performed. The Reading Center manual should be referenced for detailed instructions
  - Humphrey visual fields
  - [REDACTED]
  - [REDACTED]
  - MNREAD
- Blood draw for clinical laboratory evaluations
  - [REDACTED]
  - Serum  $\beta$ -HCG, as applicable (sample taken only for female subjects of childbearing potential)

- [REDACTED]
- [REDACTED]
- Dispense masked study drug and Study Drug Dosing Diary, and review administration instructions
  - TID dosing 10 mg/kg, 10 mg/kg, 20 mg/kg (morning, midday, evening)
  - The first dose of study drug should be administered in the clinic *after* completion of all other assessments and procedures required at this visit
- Schedule Visit 3

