## 8.2 Visit 8 (Week 144±28 Days – End of Treatment/Start of Sub-study)

The subject will return to the site for Visit 8 (Week 144). Additionally, any subject who discontinues early from the parent study should complete the Visit 8 assessments and return in 4 weeks for follow-up assessments.

This visit will be considered the end of the parent study and the beginning of the sub-study. Subjects should have taken their final dose of study drug for the parent study the night before the clinic visit.

Visit 8 will proceed as follows:

- Record any adverse events occurring since last visit and any that occur during this visit
- Record any changes in concomitant medications
- Collect any unused study drug
- Study Drug Dosing Diary review and collection: The diary will be collected and reviewed
- Physical examination
- Height and weight
- Vital signs (including systolic and diastolic blood pressure, radial pulse rate, and body temperature): performed after the subject has been in a sitting position for 3 - 5 minutes
- Complete the following ophthalmological assessments:
  - [REDACTED]
  - Ophthalmoscopy examination
  - BCVA and refraction
  - Slit-lamp examination - Slit-lamp examination should precede [REDACTED] measurement.
  - Slit-lamp photography. The Reading Center manual should be referenced for detailed instructions regarding macro photography.
  - OCT/Fundus photography - Anterior and posterior segment OCT and fundus photography will be performed. The Reading Center manual should be referenced for detailed instructions.
  - Humphrey visual fields
  - [REDACTED]

- [REDACTED]
- MNREAD
- Blood draw for clinical laboratory evaluations:
  - Hematology and biochemistry
  - Serum  $\beta$ -HCG, as applicable (sample taken only for female subjects of childbearing potential)
  - [REDACTED]
- Urinalysis
- No study drug will be dispensed at this visit for subjects that do not consent to the sub-study. Subjects not continuing into the sub-study should return to the clinic in 4-weeks ( $\pm 7$  days) for their Follow-up visit.

For all subjects that choose to participate in the open-label sub-study, in addition to the Visit 8 assessments listed above, the following will need to be completed:

- Obtain written informed consent/assent
- Dispense open-label ataluren and Study Drug Dosing Diary, and review administration instructions
  - TID dosing 10 mg/kg, 10 mg/kg, 20 mg/kg (morning, midday, evening)
- Schedule Visit 9 in 24 weeks  $\pm 28$  days

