10 MISSING DATA HANDLING

10.1 Handling Missing Efficacy Data

Missing data for the primary efficacy endpoint will be imputed through Week 48 using last observation carried forward (LOCF) as the primary method of imputation for the efficacy and ITT analysis populations.

As a sensitivity analysis to the use of LOCF, multiple imputation (using SAS PROC MI and SAS PROC MIANALYZE) will also be used to impute missing endpoint data. Missing data at week 48 will be imputed for the primary endpoint for the ITT population only. Missing data predictors will be baseline MRS, MNREAD baseline parameters of reading acuity index, critical print size, reading acuity, and subject age. Twenty iterations will be generated with a prespecified seed number of 20191015 using the Markov Chain Monte Carlo (MCMC) method.

A second sensitivity analysis will be performed using a tipping point approach. The best and worst MRS change will be selected over the entire sample. These values will be rounded to one decimal places. All ataluren-treated subjects with missing endpoint data will be imputed with the worst value and all placebo treated subjects with missing endpoint data will be imputed with the best value and a p-value derived. Next, all ataluren-treated missing values will be replaced by the next worst value all placebo-treated missing data will be replaced by the next best value and a p-value derived. This process will be continued until all ataluren-treated missing data are replaced with the best value and all placebo-treated missing data are replaced by the worst value. The point at which the p-value “tips” from non-significance to significance will be noted relative to its order and number of analyses performed. In the event that all permutations are statistically significant, then it can be concluded that imputation does not result in a false positive.

Efficacy data will not be imputed for the open-label study period.

If any needed/permitted surgical treatment is performed during the study, and as a consequence, any assessment outcomes are affected significantly due to the surgical procedure, these assessment outcomes on and after the surgery will be set as missing and the last assessment prior to the surgery will be used for later assessment time points.

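### The early-termination rule has no distance limit and keeps the last value, so exit readings up to 83 days early count as observed Week 48 and open-label values can replace true Week 48 values

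*SAP*

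**What the plan says.** The rule is in SAP section 5, in the entry on early termination, and has three steps.

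1. Window first: "Early termination would be assigned to the visit whose visit window included the termination date".
2. If the date lies in no window, "then the termination visit will be assigned to the visit closest to that date". No maximum distance and no tie rule is given.
3. "If duplicate data result from the assignment of a termination visit, then the values measured last will be selected for analysis".

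The same section fixes the Week 48 target ("End of double-masked study period is at Week 48 (day 337 ± 28 days), unless terminated early") and states that, unless otherwise defined, "baseline is the last assessment taken prior to the first study drug administration".

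The Stage 1 schedule (SAP Appendix A, Table 1) has MNREAD at Visit 2 and at Week 48 only. Exit MNREAD values should still exist, because Protocol 8.2 says that "any subject who discontinues early from the parent study should complete the Visit 8 assessments", and MNREAD is among those assessments. Open-label ataluren is dispensed at Visit 4 (Protocol 8.1.1.4).

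SAP 10.1 uses last observation carried forward (LOCF) as the primary imputation. Multiple imputation and a tipping-point analysis are the sensitivity analyses, and both act on missing endpoint data. For multiple imputation, "Missing data at week 48 will be imputed for the primary endpoint for the ITT population only". SAP 7.7 calls for sensitivity analyses only if Week 48 assessments are missing.

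**The concern.** A subject who leaves during Stage 1 will normally have one post-baseline value of the primary measure, the one taken at exit. The termination rule decides which visit that value belongs to, and so whether Week 48 counts as observed or missing.

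A nearest-visit fallback with no limit can call a value Week 48 well before the visit window opens. Keeping the value measured last can displace a value taken on schedule. The rule is not confined to Stage 1, so it also covers subjects who leave soon after the switch to open-label drug. For them, a value taken on ataluren could stand as the Week 48 result of the placebo arm.

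**Working it through.** **Inputs.** Visit days are 1, 169±28 and 337±28 (SAP Appendix A, Table 1) and 505±28 (Table 2). The baseline window is one day either side (Protocol, "Visit 2 (Baseline, Week 1 ±1 Day").

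**Reproducing the plan's days.** Target day = 7 × week + 1. Week 24: 7 × 24 + 1 = 169. Week 48: 7 × 48 + 1 = 337. Week 72: 7 × 72 + 1 = 505. All three match. The Week 48 window is 337 − 28 = 309 to 337 + 28 = 365.

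**Cut-offs for the nearest visit**, taking all scheduled visits: (1 + 169)/2 = 85, (169 + 337)/2 = 253 and (337 + 505)/2 = 421. Each of these three days is a tie that the SAP does not resolve.

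| Termination day | Assigned to | By |
|---|---|---|
| 1–2 | Visit 2 | window |
| 3–84 | Visit 2 | nearest |
| 86–140 | Week 24 | nearest |
| 141–197 | Week 24 | window |
| 198–252 | Week 24 | nearest |
| 254–308 | Week 48 | nearest |
| 309–365 | Week 48 | window |
| 366–420 | Week 48 | nearest |

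**Days 254–308.** The earliest value is 337 − 254 = 83 days before target and 309 − 254 = 55 days before the window opens. LOCF would carry this value to Week 48 anyway, so the primary estimate does not move. But Week 48 is no longer missing, so neither the multiple imputation nor the tipping-point analysis touches the subject. Someone who leaves on Day 252 is imputed and stress-tested; someone who leaves on Day 254 is treated as observed.

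**Days 3–84.** The exit value takes the Visit 2 label and, being later, displaces the Day 1 record there. The baseline definition in the same section requires a pre-dose value. Both rules cannot govern the Visit 2 record. If the exit value counts as post-baseline, LOCF carries a real change. If it does not, LOCF has only the Day 1 value to carry, and the subject fails the efficacy population's requirement of a post-baseline value (SAP 6.3). The SAP does not say which applies.

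**After the Week 48 visit and up to Day 420.** The termination visit maps to Week 48, by window to Day 365 and by nearest visit from Day 366. It duplicates the scheduled Week 48 value, and the later one is kept. For a placebo subject seen on Day 337 and terminating on Day 420, that is 420 − 337 = 83 days of open-label ataluren. Over the permitted Week 48 window the maximum runs from 420 − 365 = 55 to 420 − 309 = 111 days.

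**Other reading of closest visit.** If only visits with MNREAD count (Days 1, 337, 673), the cut-offs are (1 + 337)/2 = 169 and (337 + 673)/2 = 505. Days 170–308 then map to Week 48, up to 337 − 170 = 167 days early. Days 3–168 map to Visit 2, and late values count up to Day 504.

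**Weight of one subject.** SAP 2.5 reduces enrolment to 24. At 2:1 the placebo arm is assumed to be 24/3 = 8, so one subject is 1/8 = 12.5%. At 36 subjects it is 1/12 = 8.3%. Children under 8 need not do MNREAD (Protocol 8.3.15), so the share among subjects with primary data could be larger.

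**The case against.** The case against is substantial, and most of it stands. The window comes first, so a termination on Days 309–365 goes to Week 48 quite properly when no scheduled value exists.

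A reader might infer four stronger things that the documents do not support:

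- *That baseline is overwritten.* The baseline definition admits only pre-dose values, and the termination rule labels visits without redefining baseline.
- *That very early leavers are given a change of zero.* This is one reading. It is equally consistent with the text to keep the Day 1 baseline and let LOCF carry the exit value.
- *That early exits labelled Week 48 distort the primary comparison.* LOCF yields the same number. Disliking that number is an objection to LOCF, which is a separate matter.
- *That none of these subjects is stress-tested.* Terminations labelled Visit 2 or Week 24 leave Week 48 missing, so both sensitivity analyses apply to them.

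It is also fair that the exact cut-offs depend on what closest visit means, and that the plan gives no expected number of terminations in any band. A careful programmer might refuse to let an open-label value stand as Week 48. But nothing in the rule tells them to, and the instruction to use the last measured value points the other way. That consequence is not answered by LOCF or by the baseline definition.

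**Conclusion.** The concern holds in this limited form, and the rule is wrong as written rather than merely short of detail. Followed exactly, it can replace a true Week 48 value with one taken on open-label ataluren as late as Day 420. That is the only one of the three consequences that changes the primary comparison outright. The Days 254–308 band weakens the sensitivity analyses only. The Days 3–84 band is a conflict between two definitions that could lead two programmers to different results.

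These bands assume that all scheduled visits are candidates for the closest visit; counting MNREAD visits only widens them. The effect on the treatment estimate cannot be given, because the number of terminations is unknown. The 12.5% is one subject's share of an assumed 8-subject placebo arm and not a bias.

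**What to change.** Amend the early-termination entry in SAP section 5:

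- Accept a termination value as Week 48 only if it falls on Days 309–365, was taken before any open-label dose, and no scheduled Week 48 value exists. A scheduled value always stands.
- Never assign a post-dose value to Visit 2.
- If there is no scheduled or acceptable termination value, treat Week 48 as missing and include the subject in both the multiple imputation and the tipping-point analysis. Keep an exit value taken before any open-label dose as a dated post-baseline value, available to LOCF and counted for the efficacy population.
- State a tie rule for the remaining visits.

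I would not add the exit value to the multiple-imputation model as a predictor. Subjects who left before Week 48 have no Week 48 value from which to estimate that relation.

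The cost is a few SAP sentences before unmasking and no change to data collection. The downside is slightly more imputed data in the sensitivity analyses.
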